Staff at *We Are With You* establish whether potential participants are interested in participating in the trial and if they were they provide a paper or email copy of the information sheet and pass their contact details to the trial research staff. Trial research staff contact the

young person and check they understood the information sheet and answer any queries. If the young person is considered Gillick competent full signed consent is taken. If a young person is not considered Gillick competent signed assent is taken from the young person and formal consent taken from a primary carer.

Immediately after consent the young person completes the baseline outcome measures and is immediately randomised using a remote, independent secure randomisation service to business as usual or intervention. *We are with you* are informed of the allocation and deliver the allocated intervention.

Participants can decide how they prefer the intervention is delivered, this can be in person at *We Are With You* offices, at a school or youth centre or it can be delivered remotely using video technology. Six months after randomisation the researcher contacts the young person and conducts the 6 month outcome assessment.

Sample size calculations

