To explore the process of change within the logic model we aim to assess three domains that are key targets of brief interventions. Motivation to change will be assessed using the readiness to change ruler, a single question that assesses motivational stage in adolescents (RR; (Maisto et al., 2011)). Self-efficacy will be assessed using the short Situational Confidence Questionnaire (SCQ-8;(Breslin et al., 1998)). Positive and Negative Expectancy will be assessed using a four-item expectancy measure that assesses drug effect expectancy (SUE; (Montes et al., 2019)). These instruments will be assessed at baseline and at the 6-month follow-up point and have established psychometric properties in the adolescent population.

In addition to key demographics, age, gender, ethnicity, age of first substance use, family structure that will be assessed at baseline we will use several short, validated instruments to assess potential predictors of change and identify potential subgroups within the study. These include a short assessment of family environment assessing relationships, conflict and cohesion the Brief Family relationship Scale (BFRS; (Fok et al., 2014)), anxiety using the General Anxiety Disorder Questionnaire (GAD-7; (Mossman et al., 2017)) and depression using the Personal Health Questionnaire for adolescents (PHQ-A; (Mansour et al., 2020)) and adverse child experiences using the Adverse Child Experience Questionnaire (ACEQ; (Dong et al., 2004)). All these instruments are validated for use in an adolescent population.

Proposed outcomes at each stage of the evaluation

Outcome	No. of Questions	Baseline	Month 6
Frequency of substance use (Single TLFB item)	1	✓	
Time Line Follow-Back 28-day version ¹	0		✓
Wellbeing (WEBWMS)	14	✓	✓
Quality of Life (EQ5D-5L)	5	✓	✓
Strength & Difficulties (SDQ ²)	25	✓	✓
Self-report Delinquency (SRDS ^{1,2})		✓	✓
Motivation state to change (RR)	1	✓	✓
Substance Use Expectancy (SUE)	4	✓	✓
Self-efficacy (SCQ-8)	8	✓	✓
Generalised Anxiety Scale (GAD-7)	7	✓	
Depression - Personal Health Questionnaire (PHQ-A)	8	✓	
Adverse Childhood Experiences (ACEQ)	10	✓	
Brief Family Relationships Questionnaire (BFRS)	16	✓	

¹ TLFB28 and SRDS are researcher led questionnaires rather than client self-completed

² SRDS and SDQ are YEF Core outcomes

Compliance

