The mechanism of change will be explored using a mediation model approach and incorporating motivation, self-efficacy, and expectancy at month 6, adjusted for baseline covariates. Allocated group will be included as an interaction term. Exploring factors that impact on the mechanism of change will be assessed using stepwise regression analysis to model the relationship between pre-randomisation factors and observed outcomes at 6 months, separately for the primary outcome and for percent days abstinent from substance use. Interaction terms with allocation arm will be included in the analysis, and a significance level of 0.1 will be used to determine which factors are included in the regression model. Pre-randomisation factors include gender, age, ethnicity, IMD decile, adverse childhood experiences, anxiety and depression and family cohesion.

In addition to quantitatively understanding the mechanism of action, the qualitative analysis will provide an opportunity to explore the perceptions of the intervention from the point of view of a variety of stakeholders. The analysis will allow us to explore what elements of the interventions are useful and what elements are unnecessary, issues around how the interventions are planned and implemented and the perceived barriers or facilitators of implementation in usual practice.

Through a detailed exploration of the key dimensions, we plan on stating our logic model at the start of the project, revising this during the pilot phase and revise this again at the end of the efficacy stage. The logic model will incorporate the qualitative research exploring stakeholder perceptions of acceptability and usefulness, hindrances and facilitators associated with the process and intervention but will also combine quantitative analysis exploring adherence, dosage, fidelity, and mediators associated with behaviour change. This mixed methods synthesis will enable us to understand what works, how it works, when it works and for whom it works and provide a detailed elaboration of the mechanisms and processes through which it works.

Exploring factors affecting implementation

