5. Iatrogenic and adverse events. We do not anticipate any iatrogenic effects and brief interventions are not usually associated with adverse events. We will monitor any iatrogenic or adverse events and create a reporting system. Any event that is potentially a consequence of the trial will be reviewed by the trial management group and where appropriate an independent committee, who will decide regarding continued conduct of the trial (LOW).

6. Ongoing COVID restrictions. The trial recruitment and intervention will be conducted in accordance with government and provider guidelines on working with COVID. Follow-ups will be conducted remotely using video technology to reduce both the burden on participants and contact between research staff and multiple participants (LOW).

Timeline

Dates	Activity	Staff responsible/ leading
28/02/23	YEF receive and approve amended information sheets, privacy notices & ethical approvals	Kent (NH)
01/03/23 to 31/08/24	Recruitment and baseline assessments	Kent (SC)
31/03/23	Provide YEF with Statistical analysis plan for peer review	Kent (SC/TG/NH)
31/08/23	Submit final Statistical analysis plan with peer review responses	Kent (SC)
01/09/23 to 31/08/24	Schedule and conduct participant qualitative interviews and focus groups	Kent (TG/ NH)
01/09/23 to 28/02/25	Conduct month 6 assessments	Kent (NH)
01/03/23 to 31/08/24	Schedule and conduct stakeholder qualitative interviews and focus groups	Kent (TG/ NH)
01/03/23 to 31/08/24	Assess and calculate cost data	Kent (SC)
31/01/25 to 30/03/25	Extract LPD data	Kent (NH)
31/01/25 to 30/04/25	Statistical and qualitative analysis	Kent (SC/ TG/ NH)
01/05/25 to 31/05/25	Synthesis of findings	Kent (SC/ TG/ NH)
30/05/25	Submit draft of final report	Kent (SC/TG/ NH)

31/08/25	Respond to peer review and submit final report	Kent (SC/ TG/ NH)
----------	--	-------------------

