STATISTICAL ANALYSIS PLAN

Re-Frame: Randomised Controlled Efficacy Trial of a Diversion Programme for Adolescents in Police Custody who Possess Controlled Drugs

University of Kent

Principal investigator: [name]

Re-Frame: Randomised Controlled Efficacy Trial of a Diversion Programme for Adolescents in Police Custody who Possess Controlled Drugs

Statistical analysis plan

Evaluating institution: University of Kent Principal investigator(s): [name]

Project title ¹	Re-Frame: Randomised Controlled Efficacy Trial of a Diversion Programme for Adolescents in Police Custody who Possess Controlled Drugs
Developer (Institution)	With You
Evaluator (Institution)	University of Kent
Principal investigator(s)	[name]
SAP author(s)	[name]
Trial design	Two arm, prospective, individually randomised efficacy trial
Trial type	Efficacy
Evaluation setting	Community
Target group	Young people aged 10-17 years inclusive in police custody and in possession of class B or C controlled drugs

Number of participants	370 young people	
Primary outcome and data source	Number of offences in the 6 months post-randomisation derived from the Local Police Database (LPD)	
Secondary outcome and data source	Self-Reported Delinquency (SRDS), emotional regulation (SDQ), frequency of substance use TLFB, Situational Confidence (SCQ), Motivation to change behaviour (RR), negative and positive expectancy (SUES)	

SAP version history

Version	Date	Changes made and reason for revision
1.0	13/03/23	
1.1	08/02/24	Revision to numbers recruited reduced from 438 to 370 Addition of regression equation Addition of method to derive effect size

Table of contents

SAP VERSION HISTORY2
TABLE OF CONTENTS
INTRODUCTION
INTERVENTION4
DESIGN OVERVIEW
SAMPLE SIZE CALCULATIONS OVERVIEW7
RANDOMISATION AND BLINDING8
DATA QUALITY AND MANAGEMENT8
ANALYSIS9
PRIMARY OUTCOME ANALYSIS9
SECONDARY OUTCOME ANALYSIS10
FURTHER ANALYSES10
INTERIM ANALYSES AND STOPPING RULES11
LONGITUDINAL FOLLOW-UP ANALYSES11
IMBALANCE AT BASELINE11
LEVELS OF CONFIDENCE AND P-VALUES

Introduction

The trial is a mixed methods prospective, individually randomised efficacy trial with equal probability of being allocated to one of two arms, the Reframe intervention or business as usual.

A pilot evaluation of the Reframe intervention was conducted and recruited 76 participants. In the pilot evaluation we set several a priori parameters that would indicate whether an efficacy study was feasible.

Criteria			

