Three exploratory analyses will be undertaken.

The mechanism of change will be explored using a mediation model approach and incorporating motivation (RR), self-efficacy (SCQ-8), and expectancy (SUE) at 6-months, adjusted for baseline covariates. Allocated group will be included as an interaction term.

Stepwise regression analysis will be performed to model the relationship between prerandomisation factors; age, gender, ethnicity, IMD, BFRS, ACEQ, GAD-7, PHQ-9 and observed outcomes at 6 months, separately for the primary outcome and PDA substance use. Interaction terms with allocation arm will be included in the analysis, and a significance level of 0.1 will be used to determine which factors are to be included in the regression model. Prerandomisation factors will include gender, age, ethnicity, IMD decile, adverse childhood experiences, anxiety and depression and family cohesion. This analysis will be augmented by an additional analysis including participants in the intervention arm only using the same prerandomisation factors but also including process measures of adherence, intervention fidelity, therapeutic alliance, interventionist, and interventionist perceptions.

Interim analyses and stopping rules

No interim analyses are planned.

Longitudinal follow-up analyses

Proposed outcomes at each stage of the evaluation

Assessments are conducted at baseline and then at six months post-randomisation, the latter being the primary endpoint. Table 2, indicates outcomes assessed at each end-point.

Outcome	No. of Questions	Baseline	Month 6
Frequency of substance use (Single TLFB item)	1	~	
Time Line Follow-Back 28-day version ¹	0		\checkmark
Wellbeing (WEBWMS)	14	~	~
Quality of Life (EQ5D-5L)	5	\checkmark	\checkmark
Strength & Difficulties (SDQ ²)	25	~	~
Self-report Delinquency (SRDS ^{1,2})		~	\checkmark
Motivation state to change (RR)	1	~	~
Substance Use Expectancy (SUE)	4	~	\checkmark
Self-efficacy (SCQ-8)	8	~	\checkmark
Generalised Anxiety Scale (GAD-7)	7	\checkmark	
Depression - Personal Health Questionnaire (PHQ-A)	8	~	
Adverse Childhood Experiences (ACEQ)	10	\checkmark	
Brief Family Relationships Questionnaire (BFRS)	16	\checkmark	

 1 TLFB28 and SRDS are researcher led questionnaires rather than client self-completed 2 SRDS and SDQ are YEF Core outcomes

Imbalance at baseline

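### After randomisation the mediators are measured only at month 6, when the outcome window has closed, so the exploratory mediation analysis cannot tell mechanism from reverse causation

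*SAP*

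**What the plan says.** The SAP (Further analyses) describes three exploratory analyses. The first is a mediation model "incorporating motivation (RR), self-efficacy (SCQ-8), and expectancy (SUE) at 6-months, adjusted for baseline covariates", with allocated group as an interaction term. The Protocol repeats this under Analysis and under Exploring Adaptation. In none of these places does the mediation sentence name its dependent variable. The stepwise regression described next is run separately for the primary outcome and for percent days abstinent (PDA), so those are the natural candidates.

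On timing, the Protocol (Secondary outcomes) says of the three mediator instruments: "These instruments will be assessed at baseline and at the 6-month follow-up point". The SAP (Longitudinal follow-up analyses) agrees: "Assessments are conducted at baseline and then at six months post-randomisation, the latter being the primary endpoint". The Protocol (Participants) places the interview: "Six months after randomisation the researcher contacts the young person and conducts the 6 month outcome assessment". The primary outcome is the number of police-recorded offences in the six months after randomisation.

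On use, Exploring Adaptation feeds the mediators into a revision of the logic model, as part of a synthesis meant to "enable us to understand what works, how it works, when it works and for whom it works". In Table 4 the Adaption row gives the purpose of the mediation analysis as understanding mechanisms of change and refining the theory of change. The same row describes baseline factors as doing the mediating.

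**The concern.** A mediator must change after allocation and before the outcome it is said to influence. Here the order is reversed or, at best, simultaneous: motivation, confidence and expectancy are recorded when the offence count is already complete.

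Reverse causation is plausible on the Protocol's own reasoning. Its background section treats arrest as a moment that can prompt behaviour change, and the primary outcome includes arrests, cautions and charges. An outcome event in months 0 to 6 could therefore shift the month-6 mediator score. If the intervention reduced offending by any other route, fewer arrests could produce a difference in motivation that the model would report as an indirect effect.

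What is at stake is the account of how the intervention works and the logic-model revision built on it. The estimate of whether it works does not depend on this analysis.

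**Working it through.** **1. Time order.**

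| Measure | When taken or period covered | Source |
|---|---|---|
| RR, SCQ-8, SUE (after randomisation) | at the month-6 interview | Protocol, Secondary outcomes; SAP, Longitudinal follow-up analyses |
| Police-recorded offences | month 0 to month 6 | SAP, title table |
| SRDS | six months before the interview | Protocol, Secondary outcomes |
| PDA from TLFB28 | 28 days before the interview | Protocol, Secondary outcomes |

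The part of each outcome window that follows the mediator measurement is zero. Baseline mediator values precede allocation, so they cannot carry its effect. The therapeutic alliance scale after session two is completed in the intervention arm only and measures a different construct. The two sessions are one week apart, but no mediator is measured between them and month 6.

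**2. The plan's own figures.** None is given for the mediation analysis. The primary sample size reproduces: 2 × (1.96 + 0.8416)² / 0.3² = 174.4, so 175 per arm and 350 in total; 350 / 0.95 = 368.4, so 369, or 370 with equal arms. The point does not depend on these figures.

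**3. Does baseline adjustment protect against reverse causation?** This is an illustrative simulation; apart from the 0.3 SD effect and the sample size, its inputs are assumptions not found in the documents. Variables are standardised. Allocation lowers offences by 0.3 SD. Baseline offences predict later offences with coefficient 0.4 and the baseline mediator predicts the month-6 mediator with coefficient 0.5. The mediator has no effect on offences. Offences change the month-6 mediator by c. Both models adjust for baseline mediator and baseline offences. N = 326, from the pilot's 88% interview follow-up (0.88 × 370 = 325.6), with 4,000 repetitions per setting.

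The spurious share can also be found directly. The allocation-to-mediator path is −0.3c and the mediator-to-offences path is 0.84c / (0.84c² + 0.75 − c²). Spurious proportion mediated = 0.84c² / (0.84c² + 0.75 − c²). At c = −0.2 this is 0.0336 / 0.7436 = 4.5%.

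| c | Mediator-outcome path significant | Both paths significant | Spurious proportion mediated |
|---|---|---|---|
| 0 | 5% | 0.2% | 0% |
| −0.1 | 49% | 3% | 1% |
| −0.2 | 97% | 10% | 5% |
| −0.3 | 100% | 16% | 10% |
| −0.5 | 100% | 37% | 30% |

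With N = 370 the results are nearly the same. Baseline adjustment does not remove the artefact.

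**4. Is any correctly ordered outcome obtainable?** The Protocol's Timeline has efficacy recruitment from 01/03/23 to 31/08/24, month-6 assessments from 01/09/23 to 28/02/25, and the line "Extract LPD data" dated 31/01/25 to 30/03/25. Police data available after month 6, for the first and last efficacy recruits:

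- Extract on 30/03/25: 18.9 and 1.0 months, midpoint about 10 with even recruitment.
- Extract on 31/01/25: 17.0 and −0.9 months, so the last recruits have not yet reached month 6.

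The 76 pilot participants (76 / 370 = 21%) are outside this range. Their primary outcome was already available, so later offences may need a new pull.

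**The case against.** The SAP labels the analysis exploratory, and no efficacy estimate, test or sample size rests on it. The Protocol's objective 3 attaches the elaboration of mechanisms to the prognostic model, and Exploring Adaptation treats mediation as one strand of a synthesis with qualitative, fidelity, dosage and adherence data. All this stands and limits the importance of the point. It does not remove it, because Exploring Adaptation and Table 4 both link the mediation analysis to mechanism and theory of change, and neither document mentions time order or plans a sensitivity analysis for it.

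The size of any distortion is unknown. A mediation claim needs both paths, and for reverse effects up to 0.3 SD the spurious share in the simulation is at most about 10%. A reader might infer that the reported indirect effect will be badly wrong or could take either sign. The documents give no basis for that, and in this simulation the artefact always has the same sign as the total effect.

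A reader might also infer that offences dated after month 6 would settle the mechanism. They would restore time order only. Offences in months 0 to 6 are affected by allocation and may affect both the month-6 mediator and later offending. Adjusting for them does not in general identify an indirect effect, and the allocation-to-mediator path would still include any route through early offending. Police records are also imperfect. In a further illustrative simulation (N = 326, c = −0.3, no mediator effect on later offending, adjustment for recorded month 0–6 offences), the mediator-outcome path was falsely significant in 5% of trials with perfect recording, 18% at reliability 0.7 and 38% at 0.5. The last two figures depend on how strongly early offending is assumed to predict later offending.

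**Conclusion.** The point holds for the direction of effect. As scheduled, the mediation model can show that month-6 motivation, confidence or expectancy is associated with offending or substance use over the preceding period. It cannot show that the mediator came first. This follows from the visit schedule and needs no assumption about effect sizes. That the dependent variable is offences or PDA is an inference from the adjoining paragraph, but self-reported offending has the same problem.

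How much bias results depends on an unknown reverse effect; the simulated figures are a range under stated assumptions and do not predict this trial's result. It would be wrong to conclude that the efficacy finding is compromised, or that the mediators lack a baseline measurement. The correction is worth making because the documents intend a causal use that this design cannot support.

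**What to change.** **Needed.** In the SAP (Further analyses) and the Protocol (Analysis, Exploring Adaptation, Table 4):

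- Name the dependent variable of the mediation model.
- Report any model using month 0–6 offences, SRDS or month-6 PDA as an association whose direction is not established.
- Do not base mechanism, theory-of-change or logic-model claims on those models.
- Correct the Table 4 wording on baseline factors: a pre-randomisation factor may predict or moderate an outcome, but cannot mediate the effect of allocation.

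This costs wording only.

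**Optional, if consent and data-sharing terms allow.** In the planned police extract, also pull offences dated after each participant's month 6. Analyse them as a supplementary, time-ordered outcome with log person-time as offset and adjustment for baseline offences, age group, site, study and month 0–6 offences. State the extract date and the resulting range of follow-up, including any participants with none, and say whether pilot participants are covered. State that month 0–6 offences are an allocation-affected and imperfectly recorded confounder, set out the assumptions, and add a sensitivity analysis. The cost is an extra date range, possibly a new pull for the pilot, and unequal follow-up. Whether the data-sharing terms cover it cannot be judged from the text available.

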1. To conduct a prospective RCT to evaluate the efficacy of the intervention versus a standardised control on non-violent offences in the 6 months after randomisation and the frequency of substance use and wellbeing.
2. To conduct a micro-costing exercise to provide estimates of the cost of delivering the intervention from the perspective of the intervention delivery organisation.
3. To develop a prognostic model exploring the baseline demographics, psychological and family factors that may impact observed outcomes and using the results to elaborate mechanisms of change and where appropriate revise the intervention logic model.
4. To assess the fidelity of intervention delivery and explore the role adherence, fidelity, therapeutic alliance, interventionist factors, baseline demographic and psychological factors play in the outcomes observed for the intervention group.
5. To conduct a latent class analysis to explore potential interactions between population subgroups, intervention received, and outcomes observed.
6. To explore generalisability and inclusivity using a comprehensive cohort approach.
7. To explore the participant, police, and intervention provider perspectives on the acceptability of the referral process and intervention delivery and to explore key facilitators and hindrances to successful scaling-up of the intervention.
8. If the intervention is found to be effective, to develop a protocol for the scaling up and wider scale delivery of the intervention.

Design

Table 1: Trial design

Trial design, including number of arms		Two-arm individually randomised efficacy trial
Unit of randomisation		Young person
Stratification variables (if applicable)		Age group (10-14 years; 15-17 years) Police Force (Kent, Wigan, Sefton, Cornwall)
Primary outcome	variable	All offences 6 months post-randomisation
	measure (instrument, scale, source)	Local Police Database
Secondary outcome(s)	variable(s)	Self-reported offences, emotional regulation, substance use frequency, psychological health and well-being, situational confidence, readiness to change, expectancies.
	measure(s) (instrument, scale, source)	Self-Report Delinquency Scale (SRDS), Strengths and Difficulties Questionnaire (SDQ), Timeline Follow-Back (TLFB28), Warwick-Edinburgh Mental Well-being Scale (WEMWBS), Short Situational Confidence Questionnaire (SCQ-8), Readiness to Change Ruler (RR), Substance Use Effect Expectancy Scale (SUE)

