Regression models will be adjusted by baseline values and stratification factors as covariates, estimates of differences will be generated as marginal effects, derived from bootstrapped mean differences between the groups and the 95% confidence interval. To adjust the analysis for any potential bias that may emerge because participants were recruited to the pilot or efficacy stage of the study, we will employ an individual patient data meta-analysis approach whereby a dichotomous variable indicating pilot or efficacy study is entered into the model as a fixed effect.

Sensitivity analyses will be performed using a pattern mixture approach and multiple imputation to compare the sensitivity of conclusions to varying assumptions about the missing data, particularly whether data is missing at random (MAR) or missing not at random (MNAR) this allows for an assessment of both random and systemic bias.

The usual approach to assessing adherence is to conduct a per protocol analysis, dropping those participants who did not comply with their allocated intervention. However, this approach potentially leads to an underestimate of any true effect. We will conduct a Complier Average Causal Effects (CACE) analysis using an instrumental variable framework. CACE weights the analysis by the ITT treatment effect by the proportion of adherence, this allows the estimation of unbiased treatment effects and maintains the allocation in the analysis.

Secondary outcomes will be analysed in a similar manner, adjusting for baseline values and stratification factors as covariates.

The mechanism of change will be explored using a mediation model approach and incorporating motivation, self-efficacy, and expectancy at 6-months, adjusted for baseline covariates. Allocated group will be included as an interaction term.

Stepwise regression analysis will be performed to model the relationship between pre-randomisation factors and observed outcomes at 6 months, separately for the primary outcome and PDA substance use. Interaction terms with allocation arm will be included in the analysis, and a significance level of 0.1 will be used to determine which factors are to be included in the regression model. Pre-randomisation factors will include gender, age, ethnicity, IMD decile, adverse childhood experiences, anxiety and depression and family cohesion. This analysis will be augmented by an additional analysis including participants in

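### Stepwise selection at p<0.1 over eight factors and their arm interactions exaggerates whatever it retains, and may pass a false moderator into the logic-model revision

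*SAP*

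**What the plan says.** SAP, Further analyses, opens with "Three exploratory analyses will be undertaken". One of them is a stepwise regression relating pre-randomisation factors to outcome. The SAP names eight: "age, gender, ethnicity, IMD, BFRS, ACEQ, GAD-7, PHQ-9 and observed outcomes at 6 months". The model is fitted "separately for the primary outcome and PDA substance use". On interactions it says "Interaction terms with allocation arm will be included in the analysis", and on selection "a significance level of 0.1 will be used to determine which factors" enter the model. The Protocol has the same rule under Analysis ("a significance level of 0.1 will be used to determine which factors are to be included") and again under Exploring Adaptation.

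Neither document says whether selection is forward or backward, whether interactions are candidates for every factor or only for retained ones, or how retained terms will be reported. Neither gives shrinkage, internal validation or multiplicity control for this analysis. SAP, Levels of confidence and p-values, waives multiplicity adjustment because there is one primary outcome and one comparison, which does not cover this screen. The same section sets 0.05 as the general significance level.

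Protocol objective 3 describes a prognostic model, "using the results to elaborate mechanisms of change and where appropriate revise the intervention logic model". Exploring Adaptation plans a further revision of the logic model at the end of the efficacy stage, partly to say for which young people the programme works.

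**The concern.** Two separate problems meet here.

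The first comes from selection. A term stays in the model because its estimate was large relative to its standard error in these data. Its coefficient is then too large on average, and a confidence interval computed as if the model had been fixed in advance is too narrow.

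The second is the number of looks. Each null interaction has a 10% chance of passing, and there may be eight per outcome and two outcomes.

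What is at stake is the account of who benefits. A chance interaction could be read as a subgroup in whom the programme works differently and could be written into the logic model that guides later delivery.

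**Working it through.** **Inputs.** Selection level 0.1, eight factors and two outcomes (SAP, Further analyses). Total sample 370 at 1:1 and design effect 0.3 SD (SAP, Sample size calculations overview). Pilot follow-up 88% (SAP, Introduction), so about 0.88 × 370 = 326 for PDA.

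**The plan's own figure.** The documents give no error rate for the stepwise analysis. The sample size reproduces: 2 × (1.96 + 0.84)² / 0.3² gives 175 per arm, 350 in total. 350 / 0.95 = 369, stated as 370.

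**Chance of at least one false interaction, none being real.**
- All eight are candidates, one outcome: 1 - 0.9^8 = 0.570.
- Both outcomes: 1 - 0.9^16 = 0.815 if the outcomes are independent. It falls towards 0.570 as they become perfectly correlated.
- A moderator is called only at p<0.05: 1 - 0.95^8 = 0.337 for one outcome, and 1 - 0.95^16 = 0.560 for two independent outcomes.

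**Simulation check.** 1,000 runs per setting, N = 370 and 326, eight null main effects and eight null interactions. The factors were independent, correlated at 0.3, or correlated within a psychological block only; these correlations are assumptions.
- Full model, backward and forward selection at 0.1: 52% to 61% with at least one interaction passing.
- Backward selection on a skewed count outcome: 59% to 63%.
- At least one interaction below 0.05: 29% to 36% in the full model, and 34% to 42% when read from the stepwise-selected model.
- Interactions tested only for factors whose main effect was retained (1,500 runs, N = 370): 8% with no prognostic effects, 38% with 0.1 SD per factor, 52% with 0.2 SD per factor.

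**Bias and interval width for a null interaction that is retained.**
- Given p<0.1, the chance that p<0.05 is 0.05 / 0.10 = 50%. A nominal 95% interval for such a term therefore excludes zero about half the time, against the nominal 5%.
- For an evenly split binary factor (assumed) and N = 370, the SE of the interaction is 2 / √(370 × 0.25) = 0.21 SD. To be retained it must exceed 1.645 × 0.208 = 0.34 SD. Null terms that pass average about 2.06 SE, or 2.06 × 0.208 = 0.43 SD in absolute size. Both exceed the 0.3 SD for which the whole trial is sized.

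**Can everything be fitted together?** Arm 1, factors 8 (age group counted once), interactions 8, baseline value 1, site dummies 3 and study 1 make 22 parameters besides the intercept. 370 / 22 = 17 participants per parameter, and 326 / 22 = 15 for PDA. More than two ethnicity categories would add terms.

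**The case against.** The strongest reply is that the analysis is labelled exploratory, stands apart from the primary estimate (SAP Eq. 1), and feeds the logic model only where appropriate, alongside qualitative, adherence, dosage, fidelity and mediation evidence. That stands. It limits the seriousness of the point, but it does not make the retained estimates unbiased.

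A reader might infer that the trial will more likely than not report a false moderator. The documents do not support that as a flat statement. The 57% requires all eight interactions to be candidates and retention at 0.1 to count as a finding. The SAP speaks of the level deciding which factors enter, which leaves open that interactions are tested only for retained factors, and it gives no reporting rule. A reader might also quote 81% for the two outcomes, but that assumes offending and substance use are independent.

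It is also fair to say that stepwise selection does not create the 57%: the unselected full model gave similar rates at 0.1. That figure measures eight tests at 0.1. The harm specific to selection is the exaggeration and the under-coverage shown above.

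Finally, dropping selection does not by itself solve multiplicity. Eight unselected 95% intervals still carry about a 34% chance that at least one excludes zero under the null.

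**Conclusion.** The concern holds as a cheap improvement to an exploratory analysis. Selecting at 0.1 with no shrinkage or validation biases retained terms away from zero and understates their uncertainty.

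The size of the false-moderator risk depends on how the plan is read. With no true interaction it is about 57% per outcome if all eight are candidates (57% to 81% over both outcomes), 8% to 52% per outcome if interactions are tested only for retained factors, and 34% per outcome if p<0.05 is required with all eight tested. The 8% to 52% rests on assumed correlations between factors and assumed prognostic strengths; all figures take one interaction term per factor.

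A reader might infer that the logic model will be changed by a chance finding, or that the primary result is compromised. The Protocol only permits the results to inform a revision, and the primary model does not depend on this analysis.

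**What to change.** Replace stepwise selection in SAP, Further analyses, and in the matching Protocol text with one pre-specified model per outcome. It should contain arm, all eight factors, their arm interactions and the primary-model covariates (baseline value, age group once, site, study), with no selection.

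- **Moderators.** Give one joint test of all arm interactions per outcome at 0.05, and let it gate any moderator claim. Over two outcomes the false-positive rate of the joint tests is then at most 1 - 0.95² = 9.75% if they are independent. Report every interaction with its 95% interval as hypothesis-generating only, and state the residual 34%.
- **Prognostic model.** Keep all main effects, or use penalised regression, and report bootstrap optimism-corrected performance.
- **Tidy-up.** The factor list names PHQ-9 and the assessment table PHQ-A; reconcile them. State how ethnicity is coded.

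The cost is SAP and Protocol wording and somewhat more output. No new data are needed. The models are less parsimonious and the intervals wider, most noticeably for PDA with about 326 participants expected.
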